4 STUDY PLAN

4.1 Study Design

This is a non-randomized, prospective, open-label implementation study to determine the feasibility of establishing and integrating a PGx test into clinical care. The effectiveness aims will be assessed by comparing toxicity outcomes using a historical control group without clinical genotyping. The implementation will be deployed across cancer care sites within Penn medicine in sequential fashion, starting with PCAM followed by PPMC, and LGH.

Patients with a GI malignancy initiating chemotherapy with a fluoropyrimidine (5-FU or capecitabine) and/or irinotecan will be consented to undergo *DYPD* and *UGT1A1* genotyping, the study intervention. The PGx test order will be placed by the research coordinator and signed by the medical oncologist; a blood sample will be obtained by the phlebotomist, or saliva self-collected by the patient in clinic, and sent to CAG for genotyping. Results will be returned in the Precision Medicine tab in PennChart. For patients with an actionable genotype (variants that would require a dose adjustment of 5-FU, capecitabine or irinotecan), clinical decision support (CDS) tools will alert the ordering oncologist of the PGx result and the recommended dose adjustment. The prescribing oncologist will ultimately decide the chemotherapy dose incorporating clinical and genetic factors. The efficacy and safety of this PGx-guided approach will be determined by comparing the incidence of severe treatment related adverse events to a historical control group of GI cancer patients enrolled into PMBB.

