8.2 Overview of statistical methods

Descriptive statistics (mean, SD, median, interquartile range, range, counts, and percentage) will be used to describe and compare (t-test or rank sum test for continuous variables and Fisher's exact test for categorical variables) baseline characteristics between the historical control group and PGx arms.

8.2.1 Implementation Endpoint(s):

- We will report the number and proportion of tests returned prior to the first dose of chemotherapy.
- We will report the proportion of dose modifications made in agreement with genotype-guided dosing recommendations at the first dose.
- The proportion of tests ordered compared to the number eligible for testing.

8.2.2 Secondary Endpoint(s):

1. Clinical endpoints

- a. The proportion of patients experiencing severe TRAEs will be compared in the PMBB historical control group vs. the PGx group using Fisher's exact test.

Subgroup analyses will be performed by tumor type.

- b. The relative dose intensity (RDI) will be calculated for 5-FU, capecitabine or irinotecan as the cumulative administered dose divided by the anticipated cumulative dose over the first 6 cycles. RDI will be compared in the PMBB historical control group vs. the PGx group using linear regression adjusted for sex, race, BMI, tumor type, cancer stage, line of therapy and ECOG performance status.

Subgroup analyses will be performed by tumor type.

2. Patient reported outcomes

Patient reported outcomes as assessed on a Likert scale will be reported as means (SD) and compared between the PMBB historical control group vs. the PGx group using linear regression adjusting for age, sex, race, tumor type, cancer stage, BMI, line of therapy, and ECOG performance status.

3. Patient attitudes toward PGx testing

Patient knowledge and attitudes towards PGx testing will be assessed on a Likert scale will be reported as means (SD). We will compare results by sex, race, tumor type, and insurance status by using linear regression. (See survey in Appendix 14.7)

8.2.3 Tertiary Endpoint(s):

1. Clinical endpoints in minority populations

The proportion of patients experiencing severe TRAEs will be compared in the PMBB historical control group vs. the PGx group using Fisher's exact tests, stratified by race.

2. Minor allele frequencies will be reported by ancestry for the DPYD and UGT1A1 genes.
3. Medical services utilization and costs

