		5. To determine if providing PGx test results will improve patient reported outcomes (PRO) during the first six cycles of chemotherapy.
Hypothesis	9	Providing clinicians with the ability to order a PGx test with a rapid turnaround time for results, along with specific dosing recommendations, will increase the utilization of PGx tests to guide pharmacotherapy decisions and improve patient drug related outcomes.

Section 3: Study Methods

Section	Index	Description
Trial design	10	Non-randomized, prospective, open-label implementation study to determine the feasibility of establishing and integrating a PGx test into clinical care.
Randomization	11	n/a
Sample size	12	No sample size calculation was performed for this feasibility study with pragmatic inclusion of eligible participants recruited over a 20- month period (Mar 2021- Dec 2022).
Interim analyses	13	No interim analyses planned
Timing of final analysis	14	Participants were followed until May 31, 2023, for toxicity assessments with an intention of 6-month follow-up for each participant. All analyses were performed collectively in May-June of 2024.
Timing of outcome assessments	15	Serial questionnaires assessing patient reported outcomes (PROs) for symptoms associated with to adverse events will be prospectively collected by the study team at the time of each treatment for the first 6 cycles.

Section 4: Statistical Principles

Section	Index	Description
Confidence intervals and p-value	16	
No hypothesis testing was performed for the primary outcome (feasibility) or secondary implementation outcomes (fidelity, penetrance).
 
Descriptive statistics (mean, SD, median, interquartile range, range, counts, and percentage) will be used to describe and compare (t-test or rank sum test for continuous variables and Fisher's exact test for categorical variables) baseline characteristics between the historical control group and PGx arms.
 
For the effectiveness aims, significance was set at an alpha=0.05.
 
No corrections were made for multiple testing. Confidence intervals pertaining to the odds of experiencing a severe TRAE were reported.

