Baseline patient characteristics	25	
The following information will be obtained at screening and from the patient medical record if performed as part of usual care and available in the medical record:
 
 • Signed informed consent form • Inclusion and exclusion criteria • Demographic data: age, gender, race/ethnicity • Cancer history: GI tumor type, stage, previous cancer treatments, number of lines of therapy • Routine physical examination: ECOG performance status (see Appendix 14.2), height (cm), weight (kg) • Vital signs: heart rate, blood pressure

		
• Hematology: hemoglobin, hematocrit, white blood cell count, ANC, neutrophils, eosinophils, basophils, lymphocytes, monocytes, platelets• Clinical chemistry: sodium, potassium, calcium, glucose, creatinine, BUN, AST, ALT, alkaline phosphatase, total bilirubin, albumin• Creatinine clearance (using Cockcroft-Gault formula)• Concomitant medications (including dose, unit, frequency, route of administration and indication)
--	--	---

Section 6: Analysis

Section	Index	Description
Outcome definitions	26	
1. Primary outcome: Feasibility: the number and proportion of tests returned prior to the first dose of chemotherapy.
 
2. Secondary outcomes:
 
 a. Fidelity – proportion of dose proportion of dose modifications made in agreement with the genotype guided dosing recommendations at the first dose. b. Penetrance- proportion of tests orders compared with the number of patients treated with study chemotherapy. c. Treatment-related adverse events - proportion of patients experiencing a serious chemotherapy related toxicity defined as requiring hospitalization, visit to the emergency department or oncology evaluation center (OEC). d. Relative dose intensity - cumulative dose administered divided by the anticipated cumulative dose over six cycles reported as mg/m². e. Patient reported outcomes (PROs) during the first six cycles of chemotherapy. f. Patient knowledge and attitudes towards PGx testing.

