		
proportion of patients with TRAEs were compared between the prospective and historical control groups among UGT1A1 poor metabolizers. Chi-square tests were used for all comparisons. Factors contributing to having a TRAE were evaluated using a multivariable logistic regression model adjusting for age, sex, race, tumor type, ECOG score, presence of metastases, intent of treatment, DPYD phenotype, and UGT1A1 phenotype using a stepwise approach.
 
 d. Relative dose intensity for fluoropyrimidines and irinotecan, defined as cumulative dose administered divided by the anticipated cumulative dose over six cycles reported as mg/m² was compared between variant carriers and wild-type patients (or PM vs. IM/NM for irinotecan) in the prospective cohort using t-tests. Relative dose intensity for fluoropyrimidines and irinotecan, was compared between the prospective and historical control groups in variant carriers (or PM for irinotecan) using t-tests. e. Patient reported outcomes (PROs) during the first six cycles of chemotherapy were compared in the prospective cohort between DPYD variant carriers and wild-type patients using chi-square tests in the subset that completed PROs. f. Patient knowledge and attitudes towards PGx testing were evaluated using chi-square and t-tests as appropriate.
Missing data	28	
 a. Prospective completion of chemotherapy related toxicity per the National Cancer Institute-Common Terminology Criteria for Adverse Events (NCI-CTCAE) was not feasible due to a lack of a consistent research coordinator throughout the study. In addition, the completion rate for the PROs was very low therefore we could not assign a grade to the adverse event. b. Revised definition severe toxicities from \geq Grade 3 toxicities to treatment related adverse events requiring treatment in the hospital, emergency department, or oncology evaluation center.

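### The SAP compares relative dose intensity with historical controls by an unadjusted t-test in carriers only, where the protocol specifies a covariate-adjusted regression, and neither change is declared

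*Combined protocol and SAP*

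**What the plan says.** Protocol 4.1 sets the design: "The effectiveness aims will be assessed by comparing toxicity outcomes using a historical control group without clinical genotyping". For RDI over the first six cycles, Protocol 8.2.2 item 1b compares the biobank historical controls with the PGx group by "linear regression adjusted for sex, race, BMI, tumor type, cancer stage, line of therapy and ECOG performance status". That item does not restrict the comparison to carriers.

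SAP Section 6, item 27.2d makes two RDI comparisons. The first is within the prospective cohort, by genotype. In the second, RDI "was compared between the prospective and historical control groups in variant carriers (or PM for irinotecan) using t-tests". No covariates are named for either.

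The covariates are on the baseline list in Protocol 7.4 and SAP item 25, which includes "Demographic data: age, gender, race/ethnicity", "GI tumor type, stage, previous cancer treatments, number of lines of therapy", ECOG performance status, height and weight. Collection is conditional: "if performed as part of usual care and available in the medical record". SAP item 16 also plans to describe and compare "baseline characteristics between the historical control group and PGx arms".

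**The concern.** With a historical control, nothing in the design makes the cohorts alike. The protocol dealt with this by naming factors that may affect delivered dose and adjusting for them. The SAP's t-test leaves any difference in those factors inside the estimated cohort effect. The planned baseline table would show an imbalance, but its results are not carried into the RDI analysis.

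The change is also unexplained. SAP item 17 sets out other departures: the ECOG and prior-fluoropyrimidine criteria, the endpoint time frame and the toxicity definition. It says nothing about the RDI method or population. A reader holding both documents cannot tell which analysis was intended, or why the one that controls confounding was dropped.

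**Working it through.** **1. The two texts side by side**

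| Feature | Protocol 8.2.2, item 1b | SAP item 27.2d |
|---|---|---|
| Contrast | Historical controls vs PGx group | Prospective vs historical |
| Population | No carrier restriction stated | Variant carriers (fluoropyrimidines) or UGT1A1 poor metabolizers (irinotecan) |
| Method | Linear regression | t-test |
| Covariates | Sex, race, BMI, tumor type, stage, line of therapy, ECOG | None |

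**2. Is an adjusted RDI analysis given elsewhere in the SAP?** No. The only multivariable model in item 27 is a stepwise logistic model for severe treatment-related adverse events (item 27.2c). It does not concern RDI, and cohort is not among its listed terms. Item 29 adds comparisons of treatment modification and discontinuation and a report of survival, but no RDI model.

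**3. Is the change declared?** No. It is absent from SAP item 17 and from every row of the protocol's amendment table (versions 2.0 to 6.0).

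**4. Are the covariates available?** For prospective participants, all seven (BMI from height and weight) are on the baseline list, if recorded in usual care. For the controls this is only implied, by the protocol's adjusted model and by the planned baseline comparison.

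**5. Size.** The documents state no RDI mean, SD, effect or power, so there is no RDI figure to reproduce. The only power table (Protocol Table 5) is for adverse events. It does reproduce: exact enumeration of the two-sided Fisher test at 60% vs 30% with 48 per group gives 80.0%, against 80% stated. I use it only for plausible group sizes (48, and its smallest row, 18). Protocol 8.1 expects about 50 actionable genotypes per 500 tested, for both genes together.

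*Bias, on assumed inputs.* For one binary prognostic factor, bias of the t-test = (difference in prevalence between cohorts) × (effect of the factor on RDI). The simulation has no true cohort effect, a residual SD of 1, and an adjusted model holding that factor plus 11 null terms.

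| n per cohort | Prevalence difference | Effect (SD) | Bias = product (SD) | Type I error, t-test | Type I error, adjusted |
|---|---|---|---|---|---|
| 48 | 0 | 0.5 | 0 | 5.3% | 5.0% |
| 48 | 0.10 | 0.5 | 0.05 | 6.2% | 5.3% |
| 48 | 0.20 | 0.5 | 0.10 | 7.3% | 5.3% |
| 48 | 0.30 | 0.8 | 0.24 | 18.7% | 5.2% |
| 48 | 0.40 | 1.0 | 0.40 | 41.2% | 3.9% |
| 18 | 0.30 | 0.8 | 0.24 | 9.8% | 5.2% |

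*Precision, on assumed inputs.* Suppose the covariates explain 30% of RDI variance, enter as k = 12 terms and are unrelated to cohort. With N patients in total, the ratio of adjusted to unadjusted standard error is about √[0.70 × (N − 3)/(N − k − 3)].

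- 48 per cohort: √(0.70 × 93/81) = 0.90
- 25 per cohort: √(0.70 × 47/35) = 0.97
- 18 per cohort: √(0.70 × 33/21) = 1.05

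The gain is about 10%, then 3%, then a loss of about 5%. The case for adjustment is therefore bias, not precision.

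**The case against.** The strongest reply is that the SAP asks a different question. Protocol 8.1 frames the effectiveness hypothesis in carriers, so restricting RDI to carriers may be deliberate. With about 50 carriers before splitting by gene, seven covariates, several of them multi-level, could overload the model. This stands as a reason to shorten the covariate list or use a propensity score. It is not a reason for no adjustment, and the SAP does not give it.

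A second reply is that genotype-guided starting-dose reductions may produce an RDI gap far larger than any confounding. Whether they do depends on whether the anticipated dose in the RDI denominator is the standard or the genotype-adjusted one, which the documents do not say. Adjustment would not settle that. Nor does the reply show that confounding is negligible.

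A reader might infer more than the documents support:

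- *That protocol version 4.0, by removing the ECOG and prior-fluoropyrimidine criteria, lowered deliverable dose in the prospective cohort and so created an imbalance.* The documents do not say that these patients receive less dose, and they give no eligibility criteria for the controls.
- *That adjustment would surely sharpen the estimate.* The precision check shows that it need not in small groups.
- *That the method was switched after results were seen.* The SAP is partly in the past tense and dates the analyses to May-June 2024, but nothing shows when or why the t-test was chosen.

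**Conclusion.** The point holds as an undeclared discrepancy between protocol and SAP on a secondary outcome. The method went from adjusted regression to t-test, and the population from the whole groups to carriers or poor metabolizers. In a non-randomized comparison this removes confounder control that the protocol itself chose. Whether the reported RDI difference is biased, by how much and in which direction cannot be determined from the documents. The type I error figures rest wholly on assumed imbalance and covariate effects, and they credit the adjusted model with having measured the confounder correctly. If the cohorts happen to be balanced, the t-test loses nothing in validity.

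**What to change.** In SAP item 27.2d, report for the carrier (or poor-metabolizer) comparison a linear regression of RDI on cohort, adjusted for the protocol's seven covariates. Add age, which the protocol already includes in its patient-reported-outcome and Cox models. If carrier numbers are small, use a reduced covariate list or a propensity score, stated in advance of the re-analysis and chosen without reference to the RDI results. Keep the t-test, labelled as unadjusted. In SAP item 17, record and justify the change of method and the narrowing of the population.

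Because the SAP dates the analyses to May-June 2024, this means a modest re-analysis and not a wording change alone. It depends on the covariates being available for the historical controls, which should be confirmed first, and it may widen intervals in the smallest gene-specific groups.

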Secondary Endpoints:	
 1. The proportion of patients experiencing severe treatment related adverse events (TRAEs) over the first six cycles of chemotherapy. [Time Frame: 6 cycles] 2. The relative dose intensity of 5-FU and irinotecan dosing over the first six cycles. [Time Frame: 6 cycles] 3. Patient reported outcomes (PROs) during the first six cycles of chemotherapy. [Time Frame: 6 cycles] 4. Patient knowledge about and attitudes towards PGx. [Time Frame: 6 months] 5. The incidence of patients of African ancestry experiencing TRAEs over the first six cycles of chemotherapy. [Time Frame: 6 cycles] 6. The frequency of actionable DPYD and UGT1A1 in various ancestry groups. [Time Frame: 6 months] 7. PFS and OS in patients after genotyping [Time Frame: 6 ± 2 months] 8. The costs of PGx-guided chemotherapy [Time Frame: 6 cycles]
Study Population:	
Inclusion criteria
 
 1. Male and female subjects, 18 years or older at time of study 2. Pathologically confirmed gastrointestinal malignancy for which treatment with a fluoropyrimidine and/or irinotecan is indicated 3. Able and willing to provide informed consent 4. Willing to undergo blood or saliva sampling for PGx testing and comply with all study-related procedures 5. Life expectancy of at least 6 months 
Exclusion criteria
 
 1. Prior treatment with irinotecan 2. DPYD or UGT1A1 genotype already known

	
 3. Severe renal or hepatic impairment (or unacceptable laboratory values) 4. Women who are pregnant or breast feeding, or subjects who refuse to use reliable contraceptive methods throughout the study 5. Treating physician does not want subject to participate
Phase:	N/a
Description of Sites/Facilities	
Penn Medicine sites:
 
 1. Perelman Center for Advanced Medicine (PCAM) 2. Penn Presbyterian Medical Center (PPMC) 3. Lancaster General Hospital (LGH)
Enrolling Participants:	Approximately 500-800 participants will be enrolled across the Penn Medicine sites.

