
 1. To determine if chemotherapy-induced toxicity differs by ancestry group. 2. To determine the frequency of actionable DPYD and UGT1A1 in various ancestry groups. 3. To determine if PGx testing influences progression-free (PFS) and overall survival (OS). 4. To determine the cost-effectiveness of PGx guided chemotherapy dosing. 5. To determine the association of pre-treatment plasma uracil concentrations with severe (Grade 3 to 5) fluoropyrimidine induced toxicity with the first dose. 	
 1. The proportion of patients experiencing a serious treatment relate adverse event during the first six cycles of chemotherapy stratified by self-reported ancestry. 2. Minor allele frequency of variants in DPYD and UGT1A1 reported by self-reported ancestry. 3. PFS and OS in patients at 6 ± 2 months. 4. Means and variances of cost in the genotype-guided group as compared to the historical control group (Costs of hospitalizations, treatment, PGx test, medical services) 5. Pre-treatment plasma uracil concentrations as measured by HPLC.

OBJECTIVES	ENDPOINTS
Optional Microbiome Substudy at PCAM only	
1. To determine whether the microbiome composition impacts the occurrence of chemotherapy-induced adverse events	1. The change in bacterial abundance as measured by operational taxonomic units (OTUs) 2. The change in bacterial composition or beta diversity as measured by weighted UniFrac distance

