We will obtain data from Data Analytics Center (DAC) on service utilization and costs. These will include: number of physician visits; number of emergency department visits; number of hospitalizations; length of hospital stay; number of emergency department and hospital admissions associated with drug-related adverse events; DPYD and UGT1A1

genetic testing costs; physician visit cost; emergency department visit costs; hospitalization costs; inpatient and physician-administered medication costs; and total costs. Care Everywhere will be utilized to obtain information if patients received care outside Penn Medicine. Additionally, medical records will be requested for admissions that occur outside of Penn Medicine.

We will compare utilization and costs incurred by the PMBB usual care group with utilization and costs incurred by the PGx group using Poisson regression methods (for number of visits), and linear regression methods with appropriate transformations (e.g., log-transform, winsorization) to account for skewness in utilization and cost distributions.

4. Survival Analysis

Overall survival and progression free survival at approximately six months will be compared between the PMBB historical control group vs. the PGx group by use of Kaplan-Meier estimators and log-rank tests. Cox proportional regression analysis will be performed to adjust for clinical covariates including age, sex, race, tumor type, cancer stage, BMI, and ECOG performance status.

5. Pre-treatment uracil and fluoropyrimidine associated toxicity

First, we will examine the range of pre-treatment uracil concentrations with the association of severe toxicity to determine if there is a cut-off whereby toxicity occurs. Previous studies have proposed uracil $> 16\text{g/ml}$ as highly predictive for severe toxicity, but we will validate this cut-off in our patient population.¹⁵ We will also examine whether the pre-treatment uracil levels vary in *DPYD* variant carriers. Second, we use logistic regression models to determine the risk of severe toxicity including a binary factor for uracil concentration (above and below cut-off), with adjustment for age, sex and treatment regimen.

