10.2 Risk/Benefit Assessment

10.2.1 Known Potential Risks

Blood will be drawn from all participating patients for determining the genotype prior to start of chemotherapy. Risks of venipuncture include possible bruising, infection at the site, and in rare cases, fainting. These risks are minimized by using trained personnel. The impact on clinical oncologic outcomes is unknown. Chemotherapy dose adjustments will be performed by the treating oncologist according to his or her clinical judgment.

There can also be a risk in knowing genetic information. New health information about inherited traits that may affect participating patients and or their blood relatives may be found during the research study. DPD deficiency is an autosomal recessive disease; carriers usually do not have related health problems, but they do have an increased risk of complications when treated with fluoropyrimidine therapy.²³ *UGT1A1* plays a role in the metabolism of bilirubin and is associated with hereditary hyperbilirubinemia syndromes. The *28 variant is a common cause of Gilbert syndrome.⁶ Individuals with Gilbert syndrome may experience transient elevations in unconjugated plasma bilirubin in response to various triggers (e.g., fasting, infection, or medications). Genotypes most implicated in Gilbert syndrome are *UGT1A1**28/*28 and *UGT1A1**6/*6. Crigler-Najjar syndrome type I is very rare and results from deleterious

UGT1A1 mutations that results in hyperbilirubinemia and occur early in childhood therefore the PGx testing is unlikely to result in incidental findings. However, identification of a heterozygous state may have implications for prenatal genetic counseling. The treating oncologist may choose to return these incidental findings if pertinent for clinical care. For the purposes of this current study, variants in the *UGT1A1* gene will be interpreted to guide irinotecan drug dosing.²⁴

Additionally, there is the risk of loss of privacy with storing the health and genetic data of participating patients. Very rarely health or genetic information could be misused by employers or insurance companies; however, in such events, patients may have difficulty finding or maintaining a job or insurance. Laws such as the federal Genetic Information Non-Discrimination Act (GINA) prohibit employers and health insurers from discriminating against individuals based on their genetic information. However, GINA does not protect against life insurance or long-term care insurance.

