Additional analyses	29	
 a. The number of treatment modifications (i.e., delay of treatment or dose reduction) and treatment discontinuations in the prospective cohort were compared between the DPYD variant carriers vs DPYD wild-type patients using chi-square tests. These outcomes were also compared between the prospective and historical control groups among DPYD variant carriers. These analyses were also performed for the UGT1A1 phenotype. b. Overall survival at one year was reported for the prospective and historical cohorts.
Harms	30	No harms of the genotyping intervention were reported.
Statistical software	31	SAS version 9.4 and R version 4.2.3
References	32	
 1. Henricks LM, Lunenburg CATC, De Man FM, et al. DPYD genotype-guided dose individualisation of fluoropyrimidine therapy in patients with cancer: a prospective safety analysis. The Lancet Oncology. 2018;19(11):1459-1467. doi:10.1016/S1470-2045(18)30686-7 2. Amstutz U, Henricks LM, Offer SM, et al. Clinical Pharmacogenetics Implementation Consortium (CPIC) Guideline for Dihydropyrimidine

		
Dehydrogenase Genotype and Fluoropyrimidine Dosing: 2017 Update. Clin Pharmacol Ther. 2018;103(2):210-216. doi:10.1002/cpt.911
 
3. Fresenius Kabi. Fluorouracil Prescribing Information. Food and Drug Administration. February 2024. Accessed May 1, 2024. https://www.accessdata.fda.gov/drugsatfda_docs/label/2024/040279s030lbl.pdf
 
4. Genentech. Xeloda Prescribing Information. Food and Drug Administration. December 2022. Accessed May 1, 2024. https://www.accessdata.fda.gov/drugsatfda_docs/label/2022/020896s044s045s046s047s048s049s050s051lbl.pdf
 
5. Pfizer. Camptosar Prescribing Information. Food and Drug Administration. January 2022. Accessed May 1, 2024. https://www.accessdata.fda.gov/drugsatfda_docs/label/2022/020571Orig1s053lbl.pdf

--	--	--

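### The SAP drops PFS and the covariate-adjusted survival comparison that the protocol plans, leaving only one-year OS by cohort with no estimator, vital-status date or rationale

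*Combined protocol and SAP*

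**What the plan says.** **Protocol.** Section 3 has a tertiary objective on whether testing influences PFS and OS, with the endpoint "PFS and OS in patients at 6 ± 2 months". The synopsis lists the same endpoint as secondary. Section 8.2.3, item 4, states: "Overall survival and progression free survival at approximately six months will be compared between the PMBB historical control group vs. the PGx group". It names Kaplan-Meier estimators, log-rank tests and a Cox model with age, sex, race, tumor type, stage, BMI and ECOG. Section 7.5 and footnote 15 of the Schedule of Activities place data extraction at 6 ± 2 months, and section 7.5 counts both outcomes from treatment initiation. Section 10.2.1 says of the intervention: "The impact on clinical oncologic outcomes is unknown".

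**SAP.** The outcome definitions (item 26) and analysis methods (item 27) contain neither PFS nor OS. The one survival entry is item 29b: "Overall survival at one year was reported for the prospective and historical cohorts". Item 24 keeps extraction at six months plus two. Item 14 gives the only follow-up cut-off, and ties it to toxicity: "Participants were followed until May 31, 2023, for toxicity assessments". It adds that analyses were run in May-June 2024.

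**Rationale.** Neither the amendment log (protocol 10.9) nor SAP item 17 mentions dropping PFS, dropping the adjusted comparison, or moving to one year. The last protocol version, 6.0, is dated 14 May 2024, so section 8.2.3 was still current text when the analyses were run.

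**The concern.** The trial lowers starting doses in carriers on the expectation of less toxicity, and the protocol acknowledges that the effect on cancer outcomes is not known. PFS and OS are the endpoints that bear on this. The control group is historical, so differences in tumor type, stage or performance status between the cohorts can shift survival without any effect of testing. The protocol's Cox model was the safeguard against that, and the SAP has none for survival.

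The new horizon adds a second problem. A one-year figure can be interpreted only if the reader knows until when each patient's vital status was known and what was done with those not followed that long. The SAP states neither, for either cohort.

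The patients whose doses change are also not singled out. The SAP compares toxicity, relative dose intensity and treatment modifications within carriers or poor metabolizers, but item 29b mentions survival only by cohort.

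**Working it through.** **No survival figure to reproduce.** The documents give no sample size, event count or power for PFS or OS. The only power figures are in Table 5, for severe TRAEs. They reproduce with an exact calculation for the two-sided Fisher test (48 per group, 60% vs 30%: 80.0%), but they say nothing about survival.

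**Plans side by side**

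| | Protocol 3 and 8.2.3 | SAP item 29b |
|---|---|---|
| Endpoints | PFS and OS | OS only |
| Horizon | 6 ± 2 months | 12 months |
| Estimator and censoring | Kaplan-Meier | not stated |
| Comparison | log-rank | not stated |
| Adjustment | Cox, seven covariates | none stated |
| Carriers shown separately | no | no |

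**Horizon.** Latest extraction is 6 + 2 = 8 months after treatment starts; 12 − 8 = 4 months are not covered by the written window.

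**Share without 12 months under two possible cut-offs.** Inputs: accrual March 2021 to December 2022 (SAP item 12) and the dates in item 14. Uniform accrual is assumed, and enrolment is taken as the start of treatment.

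- Status known to 31 May 2023: patients enrolled after about the end of May 2022 fall short.
  - Accrual ending 1 December 2022: 185/641 days = 29%.
  - Accrual ending 31 December 2022: 215/671 days = 32%. In whole months, 7/22 = 32%.
  - The last patient would have about 5 to 6 months.
- Status refreshed at the 2024 analysis: from 31 December 2022 to 1 May 2024 is 16 months, so calendar time alone leaves nobody short. Only patients lost from the records would lack 12 months.

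**What a cohort-level OS figure could show about carriers.** This is an illustration that takes item 29b to mean all patients in each cohort. Section 8.1 gives about 50 actionable genotypes per 500 tested, or 10%. One-year OS of 50-80% and a loss of 10-20 points in carriers are assumed.

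- Diluted difference: 0.10 × 10 to 0.10 × 20 = 1 to 2 points.
- Power for n per group, two-sided 5%: Φ{[Δ√n − 1.96√(2p̄(1 − p̄))] / √(p₁(1 − p₁) + p₂(1 − p₂))}.
  - All patients, 500 per group: 5% (50% vs 49%) to 12% (80% vs 78%).
  - Carriers only, 50 per group: 17% (50% vs 40%) to 59% (80% vs 60%).
- Half-width of the 95% interval for a carrier difference, 1.96√(2p(1 − p)/50): 20 points at p = 0.5 and 16 points at p = 0.8.

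A carrier breakdown would therefore yield an estimate with a wide interval. It would not be a decisive test.

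**The case against.** Several stronger readings are tempting, and the documents do not support them.

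- **That one-year OS is biased upward.** This needs a crude proportion with patients of unknown status counted as alive. Item 29b says neither, and its wording is compatible with a Kaplan-Meier estimate. Excluding everyone enrolled too late would not produce this bias; excluding only survivors of unknown status while counting deaths would push the other way. Even in the count-as-alive case, with one-year OS of 70% and exponential survival assumed, the shift is small: 15/22 × 0.700 + 7/22 × 0.778 = 72.5%, or 2.5 points.
- **That nobody, or a third of patients, lacks one-year status.** The May 2023 date is a toxicity cut-off, the analysis ran a year later, and survival may be drawn from the tumor registry.
- **That the cost of dose reduction goes unexamined because of the SAP.** OS is still reported at a longer horizon, and dose intensity, modifications and discontinuations are compared in carriers or poor metabolizers. Section 8.2.3 also compared whole groups, so the carrier gap predates the SAP. Item 29b does not define its analysis set either, so whole cohorts is an inference.

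It can also be said that survival is tertiary in section 3 of a feasibility study, that PFS rests on usual-care records, and that carriers will supply few events. With 70% one-year OS, six-month OS is √0.70 = 0.84, or about 8 deaths among 50 carriers.

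These points limit the claim and its weight. They do not supply the missing PFS analysis, adjustment, estimator, vital-status date or reason for the change.

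**Conclusion.** The point holds as an unexplained departure from the protocol. PFS and the adjusted, censored comparison are absent from the SAP. The remaining item uses a horizon 4 months beyond the extraction window, with no stated method or date. The protocol's PFS/OS objective is therefore not answered as the SAP stands, and a reader who compares the two one-year figures would be making an unadjusted comparison of non-randomised cohorts.

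No direction or size of bias can be asserted. The share of patients without 12 months ranges from few or none to about 29-32%, depending on an unstated cut-off and on the uniform-accrual assumption. Survival in actionable carriers is a gap in both documents, and adding it would go beyond the protocol. The change should be made, but it does not touch the primary feasibility outcome.

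**What to change.** Rewrite SAP item 29b as follows:

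1. Restore section 8.2.3: Kaplan-Meier, log-rank and Cox with the protocol's covariates, for PFS and OS from treatment initiation. Censor OS at the date last known alive and PFS at the last disease assessment.
2. Add Kaplan-Meier estimates with confidence intervals for actionable carriers in each cohort, labelled as an addition to the protocol and as imprecise.
3. Give one-year OS only as a Kaplan-Meier estimate with numbers at risk, and state the vital-status source and cut-off date for both cohorts.
4. Record why the SAP departed from the protocol. If PFS cannot be obtained for the historical controls, say so.

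The cost is modest analysis work on outcomes that section 7.5 already provides for extracting. One-year OS additionally needs vital status beyond month 8, so it depends on whether that was collected. Carrier estimates will have wide intervals, and PFS can be no better than the usual-care records.
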